#### **3.2 Number of Subjects**

Twenty

#### **3.3 Duration of Participation**

Six months

### 3.4 Primary Study Endpoints

The primary outcome measure of efficacy will be the percent reduction of baseline Lichen Planopilaris Activity Index (LLPAI) score after 6 months of treatment defined as follows.

- Complete response: LLPAI reduction greater than 85% from baseline score.
- Partial response: LLPAI reduction of between 25-85% from baseline score.
- Non-response: LLPAI reduction of less than 25% from baseline score.

The Lichen Planopilaris Activity Index (LPPAI) is a standardized validated quantitative measure of disease activity [12]. LPPAI score (0-10) is calculated as follows: (pruritus + pain + burning)/3 + (scalp erythema + perifollicular erythema + perifollicular scale)/3 + 2.5 (pull test) + 1.5 (spreading/2). Symptoms and signs are graded on a 4-point scale with 0 = absent, 1 = mild, 2 = moderate, and 3 =severe. Clinical progression and a positive hair pull test are graded 1=yes; 0=no.

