### 1.1 Background

Lichen Planopilaris (LPP) is a form of lymphocyte mediated scarring alopecia. It is a chronic condition that predominates in women between the ages of 45-70. Patients present with discrete patches of hair loss with characteristic perifollicular erythema and scale [1]. Diffuse or localized scalp involvement may be seen. Disease progression results in irreversible hair loss and has been associated with significant impact on quality of life, depression, and anxiety [2]. Successful treatment of LPP requires clearance of the lymphocytic inflammation early in the disease course to prevent irreversible follicular destruction and permanent hair loss.

Conventional topical (e.g. corticosteroids) and systemic immunosuppressives (e.g. mycophenolate mofetil) used in the treatment of LPP directly inhibit lymphocytes but generally cannot induce clinical remission [3]. Therefore, there remains a critical unmet therapeutic need for an alternative topical product to treat LPP.

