### 3.5 Secondary Study Endpoints

The secondary outcome measures of efficacy at baseline and after 6 months of treatment will include:

- Mean follicular density as assessed using Canfield scalp photography
- Dermatology Quality of Life Index (DQLI) score : 10 standardized items measuring impact of skin disease rated as 0=not at all/not relevant; 1=a little; 2=a lot; 3=very much
- Physician Global Assessment (PGA) score : using standardized photography compared to the presenting baseline and scored as -1 = worse (no change to erythema with new areas of alopecia); 0 = no change; 1 = mild improvement (slight reduction in erythema, alopecia not progressive); 2= moderate (moderate reduction in erythema, alopecia not progressive); 3 = significant improvement (very mild erythema, alopecia not progressive); 4 = clear (no erythema, alopecia not progressive)

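### Response classes in Section 3.4 can count a participant whose alopecia is still spreading at Week 24 as a partial responder, while the PGA gives no improvement grade to progressive alopecia

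*Combined protocol and SAP*

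**What the plan says.** Section 3.4 makes the primary outcome "the percent reduction of baseline Lichen Planopilaris Activity Index (LLPAI) score after 6 months of treatment" and cuts it into three classes: "Complete response: LLPAI reduction greater than 85% from baseline score", "Partial response: LLPAI reduction of between 25-85% from baseline score" and "Non-response: LLPAI reduction of less than 25% from baseline score". None of the three refers to an individual item of the index.

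The index adds a symptom average, a sign average, a weighted pull test and a weighted spreading term. On the last two, Section 3.4 says: "Clinical progression and a positive hair pull test are graded 1=yes; 0=no". The section also states a range: "LPPAI score (0-10) is calculated as follows".

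Section 3.5 defines the PGA, a secondary endpoint. Its lowest improvement grade reads "1 = mild improvement (slight reduction in erythema, alopecia not progressive", and grades 2, 3 and 4 carry the same condition on alopecia. New areas of hair loss appear only under grade -1.

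Section 7.2 says the classes will follow the standardized scoring so that results can be set against published systemic treatments. Neither 7.2 nor 7.3 adds a rule about progression.

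**The concern.** A summed score lets one item be outweighed by the others. Here the item that records whether hair loss is advancing carries little weight, so better symptoms, milder signs or a negative pull test can produce a response label while the affected area is still growing. Section 1.1 gives the purpose of clearing the inflammation as "to prevent irreversible follicular destruction and permanent hair loss", so a reader of the response rate will want to know how many responders had stopped progressing. The plan does not call for that count.

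The stake is what the proof-of-concept result can support. The study has one open-label arm and 20 participants, and Section 7.1 expects it to give a preliminary estimate of efficacy for designing a larger study. With all 20 in the denominator, each participant who responds on the index while still spreading moves the rate by 1/20 = 5 percentage points.

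**Working it through.** **Inputs (Section 3.4).** Let S be the sum of three symptom grades (0 to 9), G the sum of three sign grades (0 to 9), P the pull test (0/1) and R spreading (0/1). I take the clinical progression grade to be the spreading item.

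LPPAI = S/3 + G/3 + 2.5 P + 1.5 (R/2)

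**The plan's own range.** The printed grading gives a maximum of 3 + 3 + 2.5 + 0.75 = 9.25, so the stated upper limit of 10 is not reproduced. It is reproduced if full spreading is worth 1.5 points: 3 + 3 + 2.5 + 1.5 = 10. I therefore checked both values.

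**Thresholds.** Partial response needs a Week 24 score from 0.15 to 0.75 times baseline. Complete response needs a score below 0.15 times baseline.

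| | Spreading worth 0.75 | Spreading worth 1.5 |
|---|---|---|
| Lowest Week 24 score with spreading | 0.75 | 1.5 |
| Baseline from which partial response is reachable | at least 0.75/0.75 = 1.0 | at least 1.5/0.75 = 2.0 |
| Baseline from which complete response is reachable | above 0.75/0.15 = 5.0 | above 1.5/0.15 = 10, so never |

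**Worked participants, all spreading at Week 24.**

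| Change from baseline | Spreading worth 0.75 | Spreading worth 1.5 |
|---|---|---|
| A. Six items moderate to mild, pull test negative, spreading at both visits | 4.75 to 2.75: 42.1%, partial | 5.5 to 3.5: 36.4%, partial |
| B. As A, but spreading is new | 4.00 to 2.75: 31.3%, partial | 4.00 to 3.50: 12.5%, non-response |
| C. Symptoms moderate to absent, signs moderate to mild, pull test negative, spreading is new | 4.00 to 1.75: 56.3%, partial | 4.00 to 2.50: 37.5%, partial |
| D. Symptoms mild, signs moderate, pull test positive, spreading; only spreading remains | 6.25 to 0.75: 88.0%, complete | 7.0 to 1.5: 78.6%, partial |
| E. Maximum score; only spreading remains | 9.25 to 0.75: 91.9%, complete | 10 to 1.5: exactly 85%, partial |

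Rows A and C show that partial response with continuing or new spreading does not depend on the value chosen. Row B does depend on it.

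**How demanding complete response with spreading is.** On the printed grading, even from 9.25 the final score must be below 0.15 × 9.25 = 1.39. Spreading uses 0.75 of that. The remaining 0.64 leaves room for one residual symptom or sign point (0.33) but not two (0.67), and the pull test must be negative. If spreading were instead graded 0 to 2, an intermediate grade of 1 would still be worth 0.75 and could still accompany a complete response; grade 2 could not.

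**Against the PGA.** Every participant in the table has milder symptoms and signs and progressing alopecia. None meets PGA grades 1 to 4, which all require non-progression. Grade -1 is worded for unchanged erythema, so it does not describe them exactly either.

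**The case against.** The LPPAI is an activity index, and Section 2 sets the objective as lowering disease activity. Partial response by its name leaves room for residual activity. A composite score and a photographic global grade may differ on one participant without either being wrong. Progression is not hidden: spreading is an LPPAI item, and the PGA and follicular density are secondary endpoints. Adding a spreading condition to the classes would also weaken the comparison with published treatments that Section 7.2 wants. The study is exploratory and descriptive.

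Most of this stands, and it is why the classes themselves should stay as they are. It does not cover the remaining gap: no table links response class to progression, so the overall rate would mix participants who stabilised with those who did not.

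Three stronger readings are tempting, and the documents do not support them.

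- *That such cases will be common.* Weighting all item patterns equally, 4,554 of 9,216 baseline patterns with perifollicular erythema and scale present (49.4%) exceed 5.0. This counts starting points from which a complete response with spreading is arithmetically possible; it is not an expected frequency.
- *That these responders are treatment failures in the protocol's own sense.* Section 4.4.1 uses that term for an investigator's judgement that another form of treatment was required. Section 1.1 says success requires clearing the inflammation, with prevention of hair loss as the purpose.
- *That a pull test turning negative shows the fault.* With spreading unchanged, 6.25 to 3.75 is a 40% fall. Without spreading the same change is 5.5 to 3.0, or 45%. That reflects the 2.5 weight and the 25% cut, not spreading.

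**Conclusion.** The point holds for partial response. Section 3.4 allows a participant with continuing or new spreading at Week 24 to be counted as a partial responder, whether spreading is worth 0.75 or 1.5 points, while Section 3.5 gives the same participant no improvement grade.

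A reader might infer that the plan readily labels progressing participants complete responders. That goes too far. It requires spreading to be worth 0.75 points, a baseline above 5.0 and nearly everything else cleared, and the printed grading behind it conflicts with the stated 0-10 range.

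The size is known per participant (5 percentage points of the response rate with 20 analysed) but not overall, because the documents give no baseline LPPAI distribution. This is a gap in endpoint definition and reporting in an exploratory study, not an error in a test. It should be settled before the data are analysed, so that the split is not a post hoc choice.

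**What to change.** - Leave the three LPPAI classes in Section 3.4 unchanged, for the comparison with published treatments.
- In Sections 3.4 and 7.2, prespecify that each class is reported split by spreading (yes/no) at Week 24.
- Define *response without progression* as at least a 25% LPPAI reduction with spreading = 0 at Week 24, and show it beside the overall response rate.
- Reconcile the 0/1 grading of spreading, which gives a maximum of 9.25, with the stated 0-10 range, and state the value used.

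The cost is a few lines of text and one extra table. The spreading item is already part of the LPPAI scored at Visit 4, so there is no new procedure or visit. The downside is a second response rate that may be lower than the first and will need a sentence of explanation.

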### 3.7 Identification of Source Data

The following source data will be directly recorded on the Case Report Form (CRF):

- Baseline and interval changes to medical history
- LLPAI score
- DQLI score
- PGA score
- Screening and documentation of Adverse Events
- Phototrichograms for hair count using Fotofinder video-epiluminescence microscopy in combination with the Trichoscan digital image analysis

The following source data will not be directly recorded in the CRF, but will be captured in supportive documentation to include study source documents and the EMR:

- Laboratory results and clinical interpretation of the values
- Standardized clinical photography

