#### **Primary Hypothesis:**

The primary endpoint for this study is the LPPAI score. While a minimal clinically significant difference for this outcome measure has not been established, clinically meaningful treatment responses will generate large changes in the LPPAI score given the weightings used in the underlying formula. Therefore, the proposed minimal accrual target of twenty patients will be adequate for the preliminary data generating purposes of an exploratory study. A larger sample size to detect smaller changes in the LPPAI score is not needed as small differences in the LPPAI score are not clinically meaningful. The minimal accrual target of 10 is achievable given an estimated incidence of LPP/FAA of 1-3% in tertiary hair loss centers. The definitions of complete response, partial response, and non-response will be defined using standardized LLPAI scoring which will permit a relative comparison of treatment efficacy to previously published systemic treatments using hydroxychloroquine and mycophenolate mofetil.

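### The LPPAI range, formula and grading in section 3.4 cannot all hold (maximum 9.25, not 10), and a patient's response category can depend on which one is corrected

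*Combined protocol and SAP*

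**What the plan says.** Section 3.4 (Primary Study Endpoints) makes three statements about how the score is built.

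- Range: "LPPAI score (0-10) is calculated as follows".
- Formula: the mean of three symptom items, plus the mean of three sign items, plus two final terms, "2.5 (pull test) + 1.5 (spreading/2" (closing bracket left off here).
- Grading: each symptom and sign runs from 0 to 3, and "Clinical progression and a positive hair pull test are graded 1=yes; 0=no".

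The same section classes each patient by percent reduction from baseline. The top class is "Complete response: LLPAI reduction greater than 85% from baseline score", a partial response is 25% to 85%, and anything below 25% is non-response.

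Section 7.2, under Primary Hypothesis, relies on the weights when it supports the accrual target: "clinically meaningful treatment responses will generate large changes in the LPPAI score given the weightings used in the underlying formula". It also says that standardized scoring will define the response classes, "which will permit a relative comparison of treatment efficacy to previously published systemic treatments using hydroxychloroquine and mycophenolate mofetil".

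Section 3.7 lists data under "The following source data will be directly recorded on the Case Report Form (CRF" (closing bracket left off). It names the LPPAI score but not its component items.

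**The concern.** The range, the formula and the grading contradict one another, and no other section gives a formula, range or spreading grade that settles the matter. If the 0 to 10 range is right and grading stays yes/no, the formula gives spreading half its intended weight. If the formula and yes/no grading are right, only the printed range is wrong.

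This matters because the endpoint is a ratio with fixed cuts at 25% and 85%. Changing the weight of one item alters numerator and denominator differently, so it does not cancel. The planned comparison with published treatments also requires this trial to weight spreading as the cited instrument does. And because the study is open-label, settling the rule after data are in hand would be a post hoc choice about the primary endpoint.

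**Working it through.** **Inputs, all from section 3.4.** Let T be the sum of the six symptom and sign items (0 to 18), P the pull test (0 or 1) and S spreading (0 or 1). One reading assumption is made: clinical progression is the spreading item, since no other grading for spreading is given.

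Score = T/3 + 2.5P + wS, with w = 1.5/2 = 0.75 as written, or w = 1.5 at full weight.

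**Step 1: try to reproduce the stated maximum of 10.**

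- As written: 18/3 + 2.5 + 0.75 = 9.25. Not reproduced.
- Halving removed, grading 0/1 kept: 6 + 2.5 + 1.5 = 10.
- Halving kept, spreading graded 0/1/2: 6 + 2.5 + 1.5 × (2/2) = 10.
- If progression is not the spreading item and spreading is instead a sign graded 0 to 3: 6 + 2.5 + 1.5 × (3/2) = 10.75. That reading does not give 10 either.

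**Step 2: does the category change?** Three examples:

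| Baseline to week 24 | w = 0.75 | w = 1.5 |
|---|---|---|
| T = 9 throughout, P = 0, spreading stops | 3.75 to 3.00, 20.0%, non-response | 4.50 to 3.00, 33.3%, partial |
| T from 9 to 6, P = 0, spreading persists | 3.75 to 2.75, 26.7%, partial | 4.50 to 3.50, 22.2%, non-response |
| T from 9 to 0, P from 1 to 0, spreading persists | 6.25 to 0.75, 88.0%, complete | 7.00 to 1.50, 78.6%, partial |

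**Step 3: general bounds.**

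- *Only spreading stops.* With the rest of the score equal to R, the reduction is w/(R + w). This is at least 25% when R ≤ 3w, so R ≤ 2.25 as written and R ≤ 4.5 at full weight. Patients with R above 2.25 and up to 4.5 are non-responders under one rule and partial responders under the other.
- *Spreading at both visits.* The lowest possible follow-up score is w, so the largest reduction is 1 − w/baseline. It exceeds 85% only if baseline > w/0.15. As written, that is a baseline above 5.0 (smallest attainable value 13/3 + 0.75 = 5.08). At full weight it is a baseline above 10, which cannot occur: the best case, 10.0 to 1.5, is exactly 85.0%, and a complete response needs more than 85%.

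**Step 4: all possible score pairs.** There are 19 × 2 × 2 = 76 states per visit. Excluding a zero baseline leaves 75 × 76 = 5,700 pairs. Comparing w = 0.75 with w = 1.5 in exact fractions:

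| Spreading, baseline to week 24 | Change from w = 0.75 to w = 1.5 | Pairs |
|---|---|---|
| yes to no | non-response to partial | 114 |
| yes to no | partial to complete | 13 |
| no to yes | partial to non-response | 114 |
| no to yes | complete to partial | 18 |
| yes to yes | partial to non-response | 30 |
| yes to yes | complete to partial | 26 |

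The total is 315 of 5,700 (5.5%). Of these, 258 cross the 25% cut and 57 cross the 85% cut. None arises without spreading at one or both visits.

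**Step 5: effect on a rate.** With 20 patients (section 3.2), one reclassified patient is 1/20 = 5 percentage points.

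**The case against.** The arithmetic is not in dispute, but its importance can be questioned on five grounds.

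1. *Limited consequence.* This is a single-arm exploratory pilot with descriptive summaries, no power calculation and no success threshold on the response rate. True, but these classes are its primary result.
2. *Few score pairs are affected.* Only 5.5% change, and a complete response with spreading at both visits is a corner case: 26 of 38 × 38 = 1,444 such pairs. This stands as a limit on size. The share is unweighted, however, so it neither predicts nor excludes several affected patients.
3. *One correction changes nothing.* If only the range is misprinted, every score and category stands. This is correct, and the documents cannot exclude it. It is a reason to check the instrument, not to leave the text alone.
4. *The two routes to 10 differ.* Under 0/1/2 grading, grade 1 still adds 0.75, and a fall from grade 2 to grade 1 could give 10.0 to 0.75, a 92.5% reduction and a complete response. This stands. The step 2 to 4 comparisons describe full weight (1.5) for any spreading, and the choice between routes must follow the instrument's own levels.
5. *Items may be kept anyway.* Section 9.2 defines source data as what is needed to reconstruct the trial, and the Data Security and Confidentiality text puts clinical findings in REDCap. Recalculation may therefore be possible. But neither place names the eight items, so it is not assured.

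**Conclusion.** The concern holds. As written, the formula and grading give a maximum of 9.25 against a stated 10, and the primary endpoint's scoring rule is internally inconsistent. Moving from the written weight to full weight can change a response category in either direction, including whether a patient with spreading at both visits can be a complete responder at all. Patients without spreading at either visit are unaffected.

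The result rests on reading clinical progression as the spreading item; the alternative 0 to 3 grading also fails to give 10. Which statement is the slip, and how many of the 20 patients would be affected, cannot be determined from the documents. The inconsistency should be resolved before any patient is scored.

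**What to change.** Check the range, the halving and the grading in section 3.4 against the cited index publication (reference 12) and amend whichever is wrong:

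- If 0 to 10 is confirmed, either keep the halving and grade spreading up to 2 using the instrument's own levels, or keep yes/no grading and delete the halving. These give different scores for an intermediate grade, so the instrument must decide.
- If the formula and yes/no grading are confirmed, correct the range to 0 to 9.25.

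State that progression and spreading are the same item, if they are. Apply one rule at every visit. Record the eight components (three symptoms, three signs, pull test, spreading) on the CRF so that the total can be recalculated.

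The cost is low: a one-line correction in section 3.4 and item-level CRF fields, with no added visits or patients.

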### 3.5 Secondary Study Endpoints

The secondary outcome measures of efficacy at baseline and after 6 months of treatment will include:

- Mean follicular density as assessed using Canfield scalp photography
- Dermatology Quality of Life Index (DQLI) score : 10 standardized items measuring impact of skin disease rated as 0=not at all/not relevant; 1=a little; 2=a lot; 3=very much
- Physician Global Assessment (PGA) score : using standardized photography compared to the presenting baseline and scored as -1 = worse (no change to erythema with new areas of alopecia); 0 = no change; 1 = mild improvement (slight reduction in erythema, alopecia not progressive); 2= moderate (moderate reduction in erythema, alopecia not progressive); 3 = significant improvement (very mild erythema, alopecia not progressive); 4 = clear (no erythema, alopecia not progressive)

### 3.6 Primary Safety Endpoints

The primary safety endpoint of this study will be the number of days between unintentional mucosal and/or ocular exposure during the study period.

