## 4.4 Early Withdrawal of Subjects

### 4.4.1 When and How to Withdraw Subjects

Patients are free to withdraw at any time and for whatever reason. No data will be collected for withdrawn subjects and withdrawn subjects may be replaced within the accrual period. There will be no follow-up for withdrawn subjects. Pre-specified reasons for discontinuing include, but are not limited to, the following:

- Patient Request: Patient decided that he/she did not want to continue (for any reason)
- Adverse Event: Patient experienced a related or unrelated event that would interfere with the study objectives/evaluation
- Lost to Follow-up: Patient did not come in for a visit and could not be reached by phone
- Treatment Failure: If in the Principal Investigator and/or Investigators' judgment, the patient's condition required another form of treatment
- Mechlorethamine sensitization: Patient develops contact dermatitis to Valchlor that cannot be managed with low potency topical corticosteroids
- Inclusion/Exclusion Discrepancy/Violation: Patient should not have been enrolled
- Noncompliance: Patient is not complying with the protocol requirements (i.e. visit schedule, dosing, regimen, etc.); a patient is to be withdrawn if he/she misses two consecutive visits
- Other: Any other reason

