### 4.4.2 Data Collection and Follow-up for Withdrawn Subjects

If a Participant withdraws from the study, no additional attempts will be made to contact the Participant.

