## **7 Statistical Plan**

### **7.1 Sample Size Determination**

Due to the pilot nature of the study, no formal statistical power or sample size calculations are necessary. The sample size of 20 patients will be sufficient for this pilot study to obtain a preliminary estimate of treatment efficacy and to generate data that will be useful in the design of a larger study.

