### **7.2 Statistical Methods**

#### **Descriptive Statistics**

Continuous variables will be summarized using the sample mean, median, standard deviation, interquartile range, and range. Categorical variables will be summarized using number and percentage of patients

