#### Adverse Event

An AE is defined as any untoward medical occurrence in a patient administered a pharmaceutical product and which does not necessarily have a causal relationship with the treatment. An AE can therefore be any unfavorable and unintended sign (including an abnormal lab finding), symptom or disease temporally associated with the use of a medicinal product, whether or not related to the medicinal product.

Each AE must be assessed by the investigator as to whether or not there is a reasonable possibility of causal relationship to Valchlor, and documented as either related or unrelated. The determination of the likelihood that Valchlor caused the AE must be provided by an investigator who is a qualified physician. .

Initial screening for AE will include non-directed questioning of the patient at each follow-up visit during the study period along with the directed questioning and examination regarding:

- Signs and symptoms of idiosyncratic allergic contact dermatitis

Patients will be instructed to stop using Valchlor and to contact the study coordinator if swelling and blistering occurs as this may represent early signs of allergic contact dermatitis. The primary investigator will then evaluate the patient and if the signs and symptoms are

compatible with allergic contact dermatitis, the patient will be offered treatment using a medium-potency topical corticosteroid to involved areas in the AM, with resumption of Valchlor application in the PM. Patients with persistent allergic contact dermatitis reactions unable to be managed as outlined above will exit the study.

- Unintentional mucosal and/ocular exposure

Patients will be warned not to apply Valchlor near eyes, mouth, or nose as it can cause pain, redness, swelling, burning, sensitivity to light, blurred vision, and blindness or permanent eye injury. If accidental Valchlor exposure to nose, mouth or eyes occurs, patients will be instructed to rinse affected areas with large amounts of water for 15 minutes and to contact the study coordinator. The primary investigator will then contact the patient to review application site instructions and schedule a follow-up evaluation if the patient reports persistent symptoms or erythema.

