### **Adverse Event Reporting Period**

For this study, the study treatment follow-up period is defined as the last scheduled visit.

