### **8.3.1 Sponsor-Investigator reporting: notifying the Mayo IRB**

The Principal Investigator and/or Investigators will report, as soon as possible, but no later than 5 working days after first learning of the problem/event, to the Mayo Clinic IRB any UPIRTSOs and Non-UPIRTSOs according to the Mayo Clinic IRB Policy and Procedures.

Documentation of adverse events will include the following information collected in the adverse event section of the case report form (and entered into the research database):

- Subject's name:
- Medical record number:
- Disease:
- The date the adverse event occurred:
- Description of the adverse event:
- Relationship of the adverse event to the research:
- If the adverse event was expected:
- The severity of the adverse event (defined by a severity scale):
- If any intervention was necessary:
- Resolution (was the incident resolved spontaneously, or after discontinuing treatment):
- Date of Resolution:

The Principal Investigator and/or Investigators will review all adverse event reports to determine if specific reports need to be made to the IRB, FDA and Actelion. The Principal Investigator and/or Investigators will sign and date the adverse event report when it is reviewed. For this protocol, only directly related SAEs/UPIRTSOs will be reported to the IRB.

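### The only named safety endpoint, days between unintentional mucosal or ocular exposures, has no value when there are zero or one exposures, and Section 7 does not resolve this

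*Combined protocol and SAP*

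**What the plan says.** Section 3.6 is a single sentence. It sets the primary safety endpoint as "the number of days between unintentional mucosal and/or ocular exposure during the study period". No other section labels a safety endpoint.

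Section 7 names neither exposure nor any safety analysis. Its general rules, in Section 7.2, are:

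- Continuous variables get the mean, median, standard deviation, interquartile range and range.
- For the rest, "Categorical variables will be summarized using number and percentage of patients".
- Missing data are not imputed.

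Section 7.1 gives one purpose of the study as "to generate data that will be useful in the design of a larger study".

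Section 8.1 makes mucosal or ocular exposure a directed question at follow-up visits and asks patients to call the coordinator when one happens. On timing it says only that "the study treatment follow-up period is defined as the last scheduled visit". The adverse event record in Section 8.3.1 includes a date field ("The date the adverse event occurred").

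On withdrawal, Section 4.4.1 states: "No data will be collected for withdrawn subjects and withdrawn subjects may be replaced within the accrual period". Section 4.4.2 adds that "no additional attempts will be made to contact the Participant". Section 7.3 keeps everyone who received study drug, but says so only for the primary analysis.

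**The concern.** An interval between exposures exists only when there are at least two. A trial in which nobody gets gel in the eye, nose or mouth would have nothing to report for its primary safety endpoint. On the within-participant reading, only people exposed repeatedly contribute, so the endpoint describes a selected few and says nothing about how many participants were affected.

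The sentence can be read in three ways: gaps within a participant, gaps across the whole trial, or time from first application to first exposure. Two analysts could therefore report different endpoints from the same data, and the choice could be made after the data are seen.

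Eye and mucosal injury is one of the five risks listed in Section 1.6. A team planning a larger study would need the proportion exposed, or a rate, with its uncertainty. The endpoint as written supplies neither.

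**Working it through.** **Inputs.** n = 20, single arm (Sections 3.1, 3.2 and 7.1); the endpoint wording in Section 3.6. The documents give no expected exposure rate and no expected value for the endpoint, so there is no figure of the plan's own to reproduce.

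**Step 1: when is there a value?** With k ordered exposure dates, the number of gaps is max(k − 1, 0). So k = 0 and k = 1 give none, k = 2 gives one, k = 3 gives two. For example, exposures on days 40 and 100 give one gap of 60 days; a single exposure on day 40 gives nothing.

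**Step 2: does the endpoint separate good outcomes from bad?** Within-participant reading, exact (Clopper-Pearson) 95% limits:

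| Outcome among 20 treated | Proportion exposed (95% CI) | Endpoint in Section 3.6 |
|---|---|---|
| Nobody exposed | 0/20 = 0% (0 to 16.8%) | no value |
| Ten exposed once each | 10/20 = 50% (27.2 to 72.8%) | no value |
| One exposed twice, 10 days apart | 1/20 = 5.0% (0.1 to 24.9%) | 10 days |

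On the trial-wide reading the second row would give 10 − 1 = 9 gaps, so it would no longer look like the first. Zero or one exposure in the whole trial would still give no value.

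**Step 3: does Section 7 repair it?**

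- The continuous summaries apply only to gaps that exist.
- Treating the rest as missing drops everyone with zero or one exposure and leaves only repeat exposures.
- The count-and-percentage rule needs a categorical variable, and Section 3.6 defines a number of days.
- The follow-up statement in Section 8.1 sets neither a start date nor a censoring rule, so it does not establish a time-to-first-exposure endpoint.

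**Step 4: how often would this bite? (illustration on assumed rates only)** Let m be the mean number of exposures per participant over the study.

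- Poisson (equal risk): p2 = P(two or more) = 1 − e^(−m)(1 + m), which is 0.00468 at m = 0.1 and 0.03694 at m = 0.3.
- Clustered (gamma-mixed Poisson, shape 0.5, assumed): p2 = 0.01106 and 0.06120.
- Chance that any of 20 has a gap: 1 − (1 − p2)^20.
- Share of exposed participants with no gap: 1 − p2/P(at least one). For Poisson, P(at least one) = 1 − e^(−m).
- Trial-wide, chance of any gap: for Poisson 1 − e^(−20m)(1 + 20m); for the clustered case the total has mean 20m and shape 20 × 0.5 = 10.

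| | m = 0.1 Poisson | m = 0.1 clustered | m = 0.3 Poisson | m = 0.3 clustered |
|---|---|---|---|---|
| Any within-participant gap | 9.0% | 19.9% | 52.9% | 71.7% |
| Exposed but no gap | 95.1% | 87.3% | 85.7% | 70.8% |
| Any trial-wide gap | 59.4% | 56.9% | 98.3% | 95.7% |

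**The case against.** The sentence is grammatically incomplete and may simply have lost its start point. If time from first application to first exposure was meant, stating the start, the censoring rule and the analysis would be enough, and the endpoint need not be replaced. This is a fair account of how the wording may have arisen, but the text does not say it and no other section implies it. The contrast between 0/20 and 10/20 does depend on the within-participant reading; across the trial, an empty result is likely only at low exposure rates.

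Exposure data are also largely captured elsewhere. Adverse events are screened at weeks 4, 12 and 24, Section 8.1 asks about exposure directly, and Section 8.3.1 has a date field. The number exposed could usually be recovered. That makes a repair feasible but does not define the endpoint. Capture is also not certain: "An AE is defined as any untoward medical occurrence in a patient administered a pharmaceutical product", so a symptom-free splash may not get a dated adverse event entry.

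The withdrawal rules affect other endpoints too. They belong here because they set the denominator: an exposure followed by withdrawal could vanish from the safety result under Section 4.4.1, and Section 7.3 protects only the primary analysis.

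Finally, this is an uncontrolled pilot with no power calculation, and Section 7.2 promises no confidence interval for any endpoint. That limits the weight of the point. Descriptive reporting still needs a variable that can be computed.

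**Conclusion.** The concern holds and should be fixed. On either gap reading the named safety endpoint has no value with zero or one exposure, and within a participant it cannot tell 0% exposed from 50% exposed once each. This follows from the definition and needs no assumed rate; the probabilities at means of 0.1 and 0.3 rest on assumed rates and an assumed degree of clustering, and only illustrate frequency. A censored time-to-first-exposure endpoint would avoid the problem, but the plan does not state one.

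The consequence is limited. No interim analysis is planned, and the stopping rule in Section 8.5 concerns contact dermatitis. What suffers is the safety report and its use in planning a larger study.

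**What to change.** - **Section 3.6:** define the primary safety endpoint as the number and proportion of treated participants with at least one unintentional mucosal or ocular exposure, with an exact 95% CI. This has a value for every possible outcome.
- **Section 7.2:** state that analysis, with all treated participants as the denominator. If timing is of interest, add time from first application to first exposure, censored at the last visit or at withdrawal.
- **Sections 4.4.1 and 7.3:** state that exposures recorded before withdrawal are kept, and that replacements are added to the withdrawn participants in the denominator and do not stand in for them.
- **Case report form:** record every reported exposure with its date, whether or not it caused symptoms.

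The cost is a few sentences in four sections and at most three fields: exposure yes/no, exposure date, and date of first application if not already captured.
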